### 2. Objectives

The proposed study consists of two aims: 1) To refine INTEGRATE-D, an intervention that offers primary care practices implementation support to align type II diabetes mellitus care with American Diabetes Association recommendations for integrating medical and psychosocial care. 2) The study will pilot test INTEGRATE-D, recruiting and randomly selecting four primary care practices to an experimental condition (i.e., treatment and control group). The study team will use mixed methods to assess the acceptability, feasibility, and cost of implementing INTEGRATE-D and to understand the preliminary impact on DMII and behavioral health process and outcome measures. The study hypothesis are:

1. Practices receiving INTEGRATE-D will find it acceptable and feasible and worth the effort and cost.
2. Practices receiving INTEGRATE-D will meet a higher number of process-of-care metrics for DMII and depression (pre-post) as compared to control practices (primary hypothesis).
3. Intervention practices will report using more quality-improving strategies post-intervention than at baseline, compared to control practices.
4. Practices receiving INTEGRATE-D will demonstrate a positive trend (improvement in PHQ-9 and HbA1c scores (pre-post) as compared to control practices (secondary hypothesis).

The anticipated methodological approaches include, chart audits, observations, surveys, and semi-structured interviews. Practice member staff and patients will be recruited from the participating sites.

### 3. Background

The American Diabetes Association (ADA) recommends integrating medical and psychosocial care (integration) to improve health outcomes for patients with comorbid diabetes mellitus (DM) and common mental and behavioral health (BH) problems. This is because when patients' depression, anxiety and diabetes distress are addressed, patients are better able to engage in self-management activities (e.g., medication adherence, physical activity, diet) and manage their DM.

In the US, 30 million people live with type II diabetes (DMII), and the majority of care for this chronic disease is delivered in primary care setting. By implementing the ADA recommendations, primary care practices can help patients manage their behavioral health needs, meet recommended goals for DMII management, and reduce the risk of adverse outcomes. In response to changes in federal and local policies and funding, some primary care practices have added staff, such as behavioral health clinicians (BHCs) and / or developed relationships with externally located BHCs, that can support integrated care for individuals with DMII.

While some practices may strive to provide integrated care per ADA recommendations, few have been able to do so comprehensively. Comprehensive change to align with ADA guidance would include systematic screening for depression and anxiety, diabetes distress, cognitive impairment

and self-management behaviors, delivering consistent treatments for DMII and for psychosocial need, and having treatment pathways for engaging BHCs and others when need is detected.

Implementing practice changes to align care with ADA recommendations could address persistent quality of care gaps and national disparities in DMII care quality and outcomes. Yet, few primary care practices have made or sustained changes to routinize integration of medical and psychosocial care for patients with DMII.

Implementing integrated care for patients with DMII involves complex practice change. This includes adopting systematic case finding and diagnosis, patient engagement/education, treatment approaches based on emerging evidence, engaging clinicians with different backgrounds (e.g., psychologists) and sometimes in different locations in treatment and following-up (including adjusting care plans) to ensure that improvement occurs and is sustained. To accomplish this, changes are needed to practice operational processes and workflows, documentation and information sharing, and communication. Multi-faceted implementation support approaches that engage leadership and multidisciplinary teams are needed to implement ADA recommendations. Effective combinations of ‘implementation strategies’ enable clinical teams to put evidence-based care in place, and involve quality reporting/feedback in combination with technical assistance, health information technology (HIT) support, and facilitation which helps practices make changes that are tailored to practices needs and resources.

#### **4. Study Design**

The study team will conduct a practice-randomized pilot study to estimate effect of the intervention on practice-level outcomes. The study team will also evaluate feasibility of recruitment, randomization, retention, assessment procedures, implementation of the INTEGRATE-D intervention and cost of doing so using mixed methods. Four practices will be recruited and randomized to either an intervention (N=2) or control arm (N=2). The study team will collect mixed methods data prior to implementation of the intervention (baseline) to assess practice capacity as well as detailed information about integrated behavioral health and DMII care processes. During implementation, a qualitative researcher will conduct monthly telephone calls with a key informant at the intervention practices. Post- intervention, the study team will collect follow-up surveys and conduct observation and interviews with intervention practices to assess what was or was not implemented and why, as well as acceptability, feasibility and perceived cost / benefits. The study team will conduct chart audits with intervention and control practices to measure key behavioral health and DMII process and outcome measures, as is commonly performed when assessing an array of behavior health integration process measures. Although this design is not optimal to conclusively demonstrate effectiveness, it is appropriate to gather preliminary evidence as to the promise of INTEGRATE-D in achieving desired outcomes.

#### **5. Study Population**

##### **i. Number of Subjects**

- i. *Primary Care Practice Sites.* The study team will recruit four practices, two rural and two non-rural practices that vary on whether they employ a behavioral health consultant. Oregon Rural Practice-based Research Network (ORPRN) practice sites that meet the eligibility criteria will participate in data collection activities that will involve surveys, observation, interviews (staff and patients), and chart audits.

- ii. *Practice Members.* Staff at all four participating practices will be invited to complete the Practice Member Questionnaire, which asks about staff demographics (e.g., gender, race/ethnicity, role, years in practice) and elements of the practice's culture that align with adaptive capacity (e.g., leadership, team-work, communication). We will use a random selection process, where practice members are stratified and randomly selected by role, to select a few (1-3) practice members from each role in the practice (e.g., clinician, office manager, medical assistant) to participate in the survey. We anticipate that 10–15 staff members per practice, depending on practice size, will be invited to complete the questionnaire. Our anticipated sample size for the proposed study will be 40-60 practice members.
- i. *Patients.* Patients with DMII diagnosis seen at least once at the practice in the 15 months prior to the intervention start date and at least once after the intervention start date will be eligible for chart audits. Because it is costly and time prohibitive to audit medical records for “all” eligible patients, the study team will randomly select 80 patients per practice from those eligible; random sampling will ensure that the results from our analyses will generalize to the sample of patients who are eligible to receive the intervention. For patient interviews, with assistance from practices, the study team will approach the 30 patients selected for chart audits about participation in semi- structured interviews. Our total sample size for the pilot study will be 320 patients across four practices.

## ii. **Inclusion and Exclusion Criteria**

### *Inclusion Criteria*

- i. Primary care practices must be affiliated with ORPRN.
- ii. Primary care practices must have more than 100 adult patients with DMII.
- iii. Patients, from the selected primary care practices, must be at least 18 years old.
- iv. Patients, from the selected primary care practices, must have a diagnosis of DMII at the time of study enrollment.
- v. Patients must be seen at least once at a participating practice in the 15 months prior to the intervention start date and at least once after the intervention start date.

## iii. **Vulnerable Populations**

Vulnerable populations will not be specifically targeted or recruited for study participation as defined by the OHSU IRB. This study will not include any vulnerable populations. We will not collect any information about subjects' status as prisoners, pregnant women, or adults lacking capacity.

## iv. **Setting**

ORPRN is a statewide practice-based research network of primary care providers, community partners, and academicians dedicated to studying health care delivery and how to improve the health of Oregonians and to reduce health disparities. ORPRN works with 279 primary care practices, including 51% that are rural and 42% provider-owned. Practices have participated in studies related to care delivery redesign, heart health, cancer prevention, and social

determinants of health. ORPRN is organized into regions, each served by a facilitator that supports improvement initiatives and collects research data.

v. **Recruitment Methods**

ORPRN's experienced recruiters will personally contact practices through a faxback process to assess interest, capacity and eligibility. ORPRN will distribute a recruitment flyer to its network of primary care practices, detailing the purpose of the study, eligibility requirements, as well as responsibilities of participating practices. Interested sites will submit a non-binding agreement to ORPRN to participate in the pilot study, either by fax or email. ORPRN and the study team will select four practices.

INTEGRATE-D aligns with programs relevant for practices in the Northwestern region (e.g., CPC+; Accountable Care Organization changes) and recruiting should not pose a challenge. Practices that agree to participate must sign a Memorandum of Understanding outlining expectations and responsibilities for participation. To encourage practice member participation, full explanation of the study and the purpose of the data collection activities will be given to practice members by the study team. For patient participation in interviews, the study team will work with a practice liaison, who will make the first contact with patients to ascertain permission to be contacted by a study member. The research team will contact them to explain the study, review the consent information sheet, and provide details of the interview. Patients will receive compensation in the form of a \$25.00 gift for their participation. Patients will be informed that the interviews are entirely voluntary. A patient sample will be drawn from the chart audits. Medical records are a secondary analysis of existing data; therefore, the study team will not recruit or seek consent from patients for the chart audits.

vi. **Consent Process**

*Modifications to the Consent Process*

- i. *Primary Care Practice Sites.* The study team will distribute informational material to practice leads of participating sites to explain the study to practice members. Additionally, the research team will be available to explain the study.
- ii. *Practice Members.* For the survey and interviews, members of the team will explain the study using an information sheet and answer any questions before data collection begins. The observation, surveys and interviews present no more than minimal risk, do not involve procedures for which consent is required outside a research context, and avoids any documentation with interviewees' names.
- iii. *Patients.* For interviews, the study team will explain the study, review the information sheet and answer any questions before conducting an interview. As with practice members, the information sheet presents no more than minimal risk and do not involve procedures for which consent is required outside a research context. The IRB submission includes a waiver of consent for patient-level data, which includes the chart audits and patient interviews, as consent is not feasible given our process for obtaining chart audits. The study team anticipates a sample of 80 chart audits per practice (320 chart audits in total). The number of charts to be reviewed renders the contact of each individual impracticable. Additionally, current contact information for potential subjects may not be available. Therefore, the time and resources needed to conduct an informed consent process are not reasonable in relation to the time to conduct the study.

## 6. Procedures Involved

As mentioned, the pilot study consists of two aims. Aim 1 is focused on the development of the intervention (i.e., INTEGRATE-D), beginning in Year 1, quarters 1 and 2. Data collection will not occur during this time as the study team will compile and refine the intervention. When the refinement period for INTEGRATE-D is complete, the study team will move to an active phase of the intervention (i.e., Aim 2), set to begin Year 1, quarter 2. Aim 2 will demonstrate the feasibility, acceptability, and cost of implementing INTEGRATE-D. See Table 1. The study team will employ mixed methods.

**Table 1. Data Collection Timeline**

Data Collection Activities	Year 1				Year 2			
	1	2	3	4	1	2	3	4
Quarter								
Semi-Structured Interviews								
Direct Observations (i.e., Site Visit Observation Guide)	X B						X F	
• Pre-Site Visit Interview	X B							
• Practice Member Staff Interviews	X B						X F	
• Interim Interviews	X	X	X	X	X	X		
• Patient Interviews							X F	
Survey Administration								
• Practice Survey			X B				X F	
• Practice Member Questionnaire			X B				X F	
Chart Audits								
• Test Chart Audits					X			
• Conduct Chart Audits							X	

*Qualitative Methodology.* The procedures for qualitative and quantitative approaches are documented as follows.

- Primary Care Practices.* In Year 1, quarter 1, the study team will randomly assign the four primary care practices to an experimental condition (i.e., treatment and control group). Following the assignments, in Year 1, quarter 3 the study team will conduct semi-structured interviews with staff at all four practices. Originally, the study team proposed site visit observations; however, due to COVID-19, semi-structured data collection will occur by phone or via web-conferencing software (i.e., Cisco Webex). Follow-up interviews will occur 15 months, post-intervention.

During the semi-structured interviews, study team members will take notes. Neither protected health information (PHI) nor identifiers will be recorded. Field notes will be prepared within 24 hours of the site visit's end. All notes will be de-identified and destroyed after the full field notes are prepared.

After the baseline interviews, the study team will also conduct interim interviews with one point of contact from each practice implementing INTEGRATE-D. The interviews will be 30- minute monthly check-in phone calls to minimize recall bias and gather real-time experiences with INTEGRATE-D. The audio recordings will be professionally transcribed, checked for accuracy and de-identified.

- ii. *Practice Member Staff.* Five to ten individuals per practice will be recruited to participate in formal and informal interviews. The study team will ask open-ended questions to explore organizational and contextual factors and discuss their experiences with delivering integrated DMII care. The interview will take about 60 minutes, and with permission, the interviews will audio-recorded. The audio recordings will be professionally transcribed, checked for accuracy and de-identified. As with the observations, the study team will return for follow-up interviews.
- iii. *Patients.* Post-intervention (Year 2, quarter 3), the study team will conduct interviews with five patients, at each practice, that were exposed to the intervention to understand patients' experiences with the practice changes that were implemented and the acceptability of those changes. Patient interviews will also consist of open-ended questions. All interviews will be audio-recorded and last approximately 60 minutes. The audio recordings will be professionally transcribed, checked for accuracy and de-identified.

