#### *Quantitative Methodology*

- i. *Chart Audits.* The study team will conduct virtual chart audits all four primary care practices (80 individuals per practice). The data will measure key behavioral health (i.e., depression), DMII process (i.e., self-management activities). The study team will conduct the audit, pre- intervention for a baseline, and 15 months post-intervention for follow-up. As noted earlier, chart audits are a secondary analysis of existing data; therefore, the study team will not recruit or seek consent from patients for the chart audits.
- ii. *Surveys.* The study team will administer two surveys during the study.

The first of which is a Practice Survey. One practice staff person (e.g., office manager, clinical lead) will complete this survey for each practice. The Practice Survey collects demographic data (e.g., ownership) and include items from the Change Process Capability Questionnaire to measure quality improvement strategies the practice uses. The survey will be administered online through RedCap.

The Practice Member Questionnaire will be administered online via Qualtrics to a select number of staff. We will ask the office manager for each practice to provide a list with employees' names, role and email addresses. The study team will use a stratified random process to select staff who will receive a survey. Staff who are selected will receive an email invitation from us to complete an anonymous online survey. We anticipate that there will be 10-15 practice members asked to complete this survey at each practice, but this will vary based on practice size and diversity of team roles. Due to COVID-19, the study team altered its initial approach, which would have taken place at an in-person all-staff meeting to collected baseline and follow-up data. For now, we are altering baseline data collection only.

For the initial submission, the study team is submitting for approval of the following qualitative and quantitative measures at baseline: the Pre-Site Visit Interview Guide, Site Visit Observation Guide, Practice Member Staff Interview, Patient Interview, Practice Survey, and Practice Member Questionnaire. As the study team refines the intervention, modifications to the IRB will be submitted.

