For the larger pragmatic hybrid implementation-effectiveness trial, the study team will extend this model to consider moderation analyses. Because we hypothesize that implementation support directly helps improve practice capacity for QI, the study team will evaluate whether practice capacity measured using Adaptive Reserve and CPCQ moderates the relationship between implementation support and distal and process of care outcomes. To do this, the study team will consider moderation analyses (e.g., heterogeneity of implementation support over time by practice capacity) by including interaction terms between study arm, time, and practice capacity in the models above.

For hypothesis 3, which compares the change in QI strategies over time between intervention and control practices, our unit of analysis is at the practice level, as only one member of the practice answers these questions. Given the low sample size (four practices each providing two surveys, resulting in eight data points), the study team will describe the change from pre to post in both groups using descriptive means, standard deviations and ranges for the overall CPCQ score and for each individual item. For the larger pragmatic hybrid implementation-effectiveness trial, we would consider a linear mixed effects model where the dependent variable would be the score (range = - 28 to +28) and fixed effects of period (post vs. pre), intervention arm (intervention vs. control) and the interaction between period and intervention plus covariates.

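### Practices are randomised two quarters before the baseline Practice Survey with no stated concealment, so the one respondent who supplies each practice's hypothesis 3 baseline may know its arm

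*Protocol*

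**What the plan says.** **Allocation.** Protocol section 6 (Qualitative Methodology) dates the randomisation: "In Year 1, quarter 1, the study team will randomly assign the four primary care practices to an experimental condition". The next sentence puts baseline staff contact later: "Following the assignments, in Year 1, quarter 3 the study team will conduct semi-structured interviews with staff at all four practices".

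**Baseline survey.** In Table 1 the Practice Survey has its baseline mark in the third quarter of Year 1 and its follow-up mark in the third quarter of Year 2. This agrees with the opening of section 6, which says of the refinement period in quarters 1 and 2: "Data collection will not occur during this time as the study team will compile and refine the intervention".

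**Measure and respondent.** The Practice Survey will "include items from the Change Process Capability Questionnaire to measure quality improvement strategies the practice uses". On who answers, the protocol says: "One practice staff person (e.g., office manager, clinical lead) will complete this survey for each practice". Section 8 makes the practice the unit of analysis for hypothesis 3, "as only one member of the practice answers these questions". Table 2 of the SAP describes 14 items, each scored from -2 to +2 by strength of agreement and summed to a range of -28 to +28.

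**What is required of baseline.** Protocol section 4 asks for baseline data before implementation, not before randomisation. Neither document describes concealment of the allocation, masking of survey respondents, or the date on which practices are told their arm.

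**The concern.** Hypothesis 3 compares the change in reported quality-improvement strategies between arms. The measure is a self-rating, and one office manager or clinical lead supplies each practice's baseline. Under the planned order, that person may already know whether the practice will receive facilitation.

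The baseline CPCQ also has a second use. Under section 8 (Rapid Qualitative Assessment), baseline summaries that include CPCQ data are prepared for the intervention practices, to guide the facilitator. A respondent who expects help has a reason to report need that a control respondent lacks. That would lower the intervention baseline and enlarge the apparent gain. Changes made in anticipation of support would raise the baseline and shrink the gain.

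With two practices per arm, such a shift can be neither detected nor adjusted for. The issue is separate from whether a survey was completed after facilitation had begun: it remains even if every baseline survey came before the first facilitation visit.

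**Working it through.** The plan gives no figure of its own for this point, so the check is one of sequence, followed by a sensitivity calculation.

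**Sequence**

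| Step | Planned time | Source |
|---|---|---|
| Random assignment | Year 1, quarter 1 | Protocol section 6, text |
| Aim 2 active phase | "set to begin Year 1, quarter 2" | Protocol section 6, opening |
| Baseline Practice Survey | Year 1, quarter 3 | Table 1 |
| Baseline staff interviews | Year 1, quarter 1 | Table 1 |
| Baseline staff interviews | Year 1, quarter 3 | Protocol section 6, text |

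The gap from assignment to the baseline Practice Survey is 3 - 1 = 2 quarters. The two sources disagree on the interviews, but this does not affect the Practice Survey row.

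**Effect on the contrast**

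Inputs from the documents: 14 items; a sum from -28 to +28 (14 × 2 = 28, so the range is 56 points); 2 practices per arm; 4 × 2 = 8 data points.

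Input assumed: knowing the arm moves each item by 0.25 to 0.5 points, all in the same direction within a practice. The documents give no value for this.

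Let *b* be the shift in a practice's baseline sum due to knowing its arm, and *f* the corresponding shift at follow-up. That practice's change score moves by *f* - *b*. An arm mean averages two practices, so with no shift in the control arm:

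bias in the difference in change = [(*f*₁ - *b*₁) + (*f*₂ - *b*₂)] / 2

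The size of *b* at one practice is 14 × 0.25 = 3.5 points, up to 14 × 0.5 = 7 points.

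| Case | Size of bias at 0.25 per item | Size of bias at 0.5 per item |
|---|---|---|
| One intervention practice shifts, *f* = 0 | 3.5 / 2 = 1.75 | 7 / 2 = 3.5 |
| Both shift the same way, *f* = 0 | (3.5 + 3.5) / 2 = 3.5 | (7 + 7) / 2 = 7 |
| Both shift, *f* = *b* | 0 | 0 |

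The largest entry is 7 / 56 = 12.5% of the scale and the smallest non-zero entry is 1.75 / 56 = 3.1%. A lowered baseline (*b* negative) inflates the intervention effect, and a raised one deflates it.

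**The case against.** **Knowledge of arm is not shown.** The documents date the assignment but not its disclosure. A reader might infer that respondents did know. The SAP (Data Collection) says that the second intervention clinic's start was delayed for its COVID response, which suggests it may have known its arm before facilitation, but this does not date its survey. A reader might also infer that some baseline surveys followed the start of facilitation: pre-intervention collection ran from November 2020 to July 2021, while facilitation began in December 2020 and June 2021. That window pools interviews and surveys and gives no dates per clinic, so it does not establish this. What stands is that knowledge was possible, not that it occurred.

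**Change scores may cancel the bias.** Respondents at intervention practices necessarily know their arm at follow-up. A stable arm-related tendency, equal at both surveys, drops out, and masking only the baseline would then leave the follow-up shift uncancelled. This is a fair point: it rules out saying that any baseline shift carries through whole. It does not remove the concern, because nothing in the documents suggests equal shifts. The baseline incentive, to show need before tailored help, has no evident counterpart after help has ended.

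**Timing was aligned between arms.** SAP Table 2 says that intervention and control clinics completed the survey at the same time. That aligns dates; it neither masks the arm nor places baseline before allocation.

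**Other measures.** A reader might extend the concern to Adaptive Reserve and the baseline interviews. The documents do not support treating them alike. Neither carries a quantitative arm contrast in this pilot, and moderation by Adaptive Reserve is reserved for the larger trial. Nor is assignment before the interviews established: Table 1 puts the baseline interviews in the same quarter as assignment.

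**The stakes are modest.** Hypothesis 2 is primary. Section 8 acknowledges the eight data points and plans only means, standard deviations and ranges, and section 4 concedes that the design cannot demonstrate effectiveness conclusively. This limits the consequence, but descriptive reporting does not remove a bias from the figures described.

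**Conclusion.** The concern holds as a matter of design order. Assignment is planned two quarters before the baseline Practice Survey, no text conceals the allocation, and one possibly arm-aware person supplies each practice's hypothesis 3 baseline.

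Under the assumed 0.25 to 0.5 points per item, the descriptive difference in change could be off by 1.75 to 3.5 points if one intervention practice shifts and by 3.5 to 7 if both do, in an unknown direction. These figures require every item to move the same way, with no shift at control practices and none at follow-up. Matching follow-up shifts would reduce them, to zero if equal. They are illustrations, not estimates of a bias that occurred.

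The point merits correction because section 4 makes assessing randomisation and assessment procedures a purpose of the pilot, and section 8 carries the CPCQ into the larger trial as an outcome and a moderator. It does not affect the primary hypothesis.

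**What to change.** 1. **Order of steps.** In Protocol section 6 and Table 1, place the baseline Practice Survey at all four practices before the allocation is drawn. If the draw must stay in quarter 1, state that each practice's arm is concealed from it until its baseline survey is submitted. This needs no new data; the cost is that practices learn their arm later. It removes the baseline source of bias only, since follow-up responses remain unmasked.
2. **Baselines already collected.** The SAP is written in the past tense, so these data cannot be re-sequenced. State for each practice when it learned its arm relative to its baseline survey. Where the survey came after disclosure, label the hypothesis 3 contrast as having an unmasked baseline. This costs a sentence or two, provided the dates are on file.
3. **Interview timing.** Reconcile Table 1, which marks baseline staff interviews in Year 1, quarter 1, with the text of section 6, which puts them in quarter 3. This is an editorial correction.
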